7.10.1 Summary of TEAEs

Separate summaries of treatment-emergent ocular and systemic AEs will be produced by treatment group presenting the number and percentages of patients experiencing at least one:

- AE,
- SAE,
- IMP-related AE (*i.e.*, related or missing relationship with the IMP),
- AE leading to premature study IMP withdrawal.

This table will be presented overall on the Azopt® safety set for TEAE for Azopt® and by treatment group on the Safety set for TEAE for LT4032 or Lumigan®

7.10.2 Details of AEs

Separate descriptions of treatment-emergent ocular and systemic AEs for Azopt® will be produced overall on Azopt® Safety set:

- Number and percentage of patients experiencing at least one TEAE, as well as the number of TEAEs, by SOC and PT. The same summary table will be produced for SAEs (if any), and AEs related to Azopt® and AEs leading to premature IMP drug withdrawal

Separate descriptions of treatment-emergent ocular and systemic AEs for LT4032 or Lumigan® will be produced by treatment group on the Safety set.

- Number and percentage of patients experiencing at least one TEAEs as well as the number of TEAEs by SOC and PT. The same summary table will be produced for SAEs, IMP-related AEs, IMP-related SAEs and AEs leading to premature IMP drug withdrawal
- Number and percentage of patients experiencing at least one TEAEs as well as the number of TEAEs by SOC, PT and severity
- Number and percentage of patients experiencing at least one TEAEs as well as the number of TEAEs by SOC, PT and relationship with IMP
- Number and percentage of patients with TEAEs by SOC, PT and maximal severity
- Number of patients with TEAEs by SOC, PT and strongest relationship

Summary of treatment-emergent non serious AEs (ocular or systemic) will be produced by treatment group, for LT4032 or Lumigan® presenting the number and percentages of patients experiencing:

- at least one non serious AE
- at least one non serious AE when percentages by PT is $\geq 5\%$ for one group,

as well as the number of these TEAEs by SOC and PT

7.10.3 Individual listing of AEs

Patient data listings of AEs (ocular and systemic together) will be produced:

- for non emergent AEs on enrolled patients
- for TEAE, serious TEAE, drug related TEAE and TEAE leading to premature IMP drug withdrawal, separately TEAE for Azopt and TEAE for T4032 or Lumigan®
- for Post-treatment AE, ie. after the day of the maximal date between last IMP instillation and Visit 4 (Week 12)

Patient data listings of COVID-19 AEs (PT: COVID-19, Coronavirus infection) will also be produced.

The following variables will be presented:

- Treatment group
- Patient's identifier
- Worse eye (Right Eye/Left eye)
- Gender
- Age at baseline (Day 1)
- Diagnosis (Verbatim)
- SOC
- PT
- Localisation
- Date / time of occurrence
- Time to occurrence (days) from the date of the first IMP instillation
- Date / time of recovery/date of death, if any
- Duration (days)
- Outcome

- Frequency and details
- Severity
- Action taken regarding the IMP
- Requirement for therapy adjustment/modification
- Requirement for surgical/medical procedure,
- Seriousness,
- Relationship with T4032/Lumigan® in the investigator's opinion,
- Relationship with Azopt® in the investigator's opinion,
- Relationship with protocol procedure.

Listings will be sorted by treatment group, patient's identifier and date of onset.

Listing of Deaths, Other Serious adverse events, discontinuations due to adverse events and other adverse events of special interest will be also provided for narratives.

Discontinuations due to adverse events include drug related AE leading to premature IMP drug OR study withdrawal (ie drug related AE with action taken = drug withdrawn OR End of study with premature discontinuation due to this AE).

8 CHANGES FROM PROTOCOL

Changes from protocol are the following:

- Regarding Safety set (Section 2.1), due to Azopt® is an IMP, Azopt® Safety Set has been added.
- Baseline definition has been completed (Section 4.3.2).
- Regarding IOPs:
 - Descriptions during the run-in period have been added (Section 5.2)
 - Descriptions during the treatment period depending on the History of glaucoma or ocular hypertension (Section 6.2.2) have been added
 - Descriptions of the mean diurnal IOP have been added (Section 6.2.2)
 - Exploratory analysis of impact of circadian rhythm on IOP have been added (Sections 6.1.4 and 6.2.1)
- Regarding COVID-19 crisis, some analyses have been added to explore the consequence on this trial:
 - Descriptions of disposition of patients (Section 5.1) and demographic and baseline characteristics (Section 5.2) for patients who prematurely discontinued the study for COVID-19 crisis and by possible impact of COVID-19 pandemic classes have been added
 - Descriptions of demographic and baseline characteristics (Section 5.2) according to the following groups have been added: Patients from ITT set included in m-ITT set versus Patients from ITT set not included in m-ITT set
 - Descriptive statistics of IOP (Section 6.1) and exploratory analysis (Section 6.1.4) on possible impact of COVID-19 pandemic classes have been added
 - Listing of patients with COVID-19 AE (Section 7.10.3)
- Regarding secondary efficacy endpoints (Section 6.2), they will be performed on PP
- Regarding subjective ocular symptoms throughout the day (Section 7.2) and subjective ocular symptoms upon instillation (Section 7.3), due to data are repeated at Week 6 and Week 12, ANCOVA models at Week 6 and Week 12 have been replaced by MMRM models
- Regarding adverse events (Section 7.10):
 - Due to a follow-up visit is performed and Azopt® is an IMP, the period of emergence for each product has been reviewed
 - Description of treatment emergent non serious AEs for LT4032 or Lumigan® have been added
 - Necessary listings of AEs have been modified

9 VALIDATION OF STATISTICAL PROGRAMMING

Validation of statistical programming will be performed in agreement with Aixial SOP.

Logs of all programs used for analysis and data preparation will be checked for errors and unexpected warnings.

Double programming of ITT population, worse/contralateral eye, derivation and analyses regarding primary endpoint (i.e., IOP) will be performed by the lead statistician. Double programming of all derived will be also performed by a third party. A third party will review all statistical outputs (tables, figures) and results from statistical tests/models, as well as SAS code of all statistical programs. This includes macros programs developed for the study.

Any undocumented updating of study data in statistical programs instead of change in clinical database (or source data) is not allowed. Specifically, this refers to the cases where patients or the data are added/changed using a statistical program rather than updating the database. This kind of hard coding is usually proposed to correct deficiencies (missing values, wrong values, and wrong measurement units) in the database when these errors are detected after database lock.

No hard coding is done in any programs used for the creation of analysis data sets, tables, listings, or analyses that are intended for external reporting after database lock (i.e., clinical study reports, publications, abstracts, etc.).

This policy ensures integrity of clinical data, since no changes are made to the study data without appropriate documentation from the investigator sites and appropriate audit trails within the clinical trial database.

APPENDIX 1. SAS SYNTAX FOR STATISTICAL MODELS PROGRAMMING

1. Main analysis of the primary efficacy endpoint (Section 6.1.1)

Mixed Model for Repeated Measures (MMRM)

The syntax with SAS using the MIXED procedure will be:

```
Proc mixed data = ... method = REML;
  Class patient treatment visit country;
  Model changeIOP = treatment visit baselineIOP washoutdur country
    treatment*visit baselineIOP*visit / ddfm = satterth solution alpha=0.05;
  Repeated visit / type = UN subject = patient;
  Lsmeans treatment*visit / pdiff cl;
  Estimate "Week 12 - Diff T4032 - Lumigan" treatment 1 -1
    treatment*visit 0 1 0 -1 / cl;
  Estimate "Week 6 - Diff T4032 - Lumigan" treatment 1 -1
    treatment*visit 1 0 -1 0 / cl;
Run;
```

2. Sensitivity analyses of the primary efficacy endpoint (Section 6.1.2)

ANCOVA considering the post-randomisation last available value (LOCF)

The syntax with SAS using the MIXED procedure will be:

```
Proc mixed data = ... ;
  Class treatment country;
  Model last_changeIOP = treatment baselineIOP washoutdur country / solution
    ddfm=satterth;
  LSmeans treatment / pdiff cl;
  Estimate "Week 12 - Diff T4032 - Lumigan" treatment 1 -1 / cl;
Run;
```

ANCOVA considering the observed value

The syntax with SAS using the MIXED procedure will be:

```
Proc mixed data = ... ;
  Class treatment country;
  Model changeIOP_W12 = treatment baselineIOP washoutdur country/ solution
    ddfm=satterth;
  LSmeans treatment / pdiff cl;
  Estimate "Week 12 - Diff T4032 - Lumigan" treatment 1 -1 / cl;
Run;
```

3. Supporting analyses to check the validity of the main analysis (Section 6.1.3)

3.1. Investigation of treatment by baseline IOP interaction

The syntax with SAS using the MIXED procedure will be:

```
Proc mixed data = ... method = REML;
  Class patient treatment visit country;
  Model changeIOP = treatment visit baselineIOP washoutdur country
    treatment*visit baselineIOP*visit treatment*baselineIOP / ddfm = satterth
    solution alpha=0.07;
  Repeated visit / type = UN subject = patient;
  Lsmeans treatment*visit / pdiff cl;
Run;
```

3.2. Investigation of treatment by wash-out duration interaction

The syntax with SAS using the MIXED procedure will be:

```
Proc mixed data = ... method = REML;
  Class patient treatment visit country;
  Model changeIOP = treatment visit baselineIOP washoutdur country
    treatment*visit baselineIOP*visit treatment*washoutdur / ddfm = satterth
    solution alpha=0.07;
  Repeated visit / type = UN subject = patient;
  LSmeans treatment*visit / pdiff cl;
Run;
```

3.3. Investigation of treatment by country interaction

The syntax with SAS using the MIXED procedure will be:

```
Proc mixed data = ... method = REML;
  Class patient treatment visit country;
  Model changeIOP = treatment visit baselineIOP washoutdur country
    treatment*visit baselineIOP*visit treatment*country / ddfm = satterth
    solution alpha=0.07;
  Repeated visit / type = UN subject = patient;
  LSmeans treatment*visit / pdiff cl slice = ;
Run;
```

3.4. Supporting analyses to check the validity of the ANCOVA

For the treatment by baseline IOP interaction, the syntax with SAS using the MIXED procedure will be:

```
Proc mixed data = ... ;
  Class treatment country;
  Model last_changeIOP = treatment baselineIOP washoutdur country
    treatment*baselineIOP / solution ddfm=satterth alpha=0.07;
  LSmeans treatment*visit / pdiff cl;
Run;
```

For the treatment by washout duration interaction, the syntax with SAS using the MIXED procedure will be:

```
Proc mixed data = ... ;
  Class treatment country;
  Model last_changeIOP = treatment baselineIOP washoutdur country
    treatment*washoutdur / solution ddfm=satterth alpha=0.07;
  LSmeans treatment*visit / pdiff cl;
Run;
```

For the treatment by country interaction, the syntax with SAS using the MIXED procedure will be:

```
Proc mixed data = ... ;
  Class treatment country;
  Model last_changeIOP = treatment baselineIOP washoutdur country
    treatment*country / solution ddfm=satterth alpha=0.07;
  LSmeans treatment*visit / pdiff cl;
Run;
```

4. Exploratory analyses of the primary efficacy endpoint analysis (Section 6.1.4)

For treatment by possible impact of COVID-19 pandemic interaction for MMRM, the syntax with SAS using the MIXED procedure will be:

```
Proc mixed data = ... method = REML;
  Class patient treatment visit country impactcovid;
  Model changeIOP = treatment visit baselineIOP washoutdur country impactcovid
    treatment*visit baselineIOP*visit treatment*impactcovid / ddfm = satterth
    solution alpha=0.07;
  Repeated visit / type = UN subject = patient;
  LSmeans treatment*visit / pdiff cl;
Run;
```

For treatment by possible impact of COVID-19 pandemic interaction for ANCOVA, the syntax with SAS using the MIXED procedure will be:

```
Proc mixed data = ... ;
  Class treatment country impactcovid;
  Model last_changeIOP = treatment baselineIOP washoutdur country impactcovid
    treatment*impactcovid / solution ddfm=satterth alpha=0.07;
  LSmeans treatment*visit / pdiff cl;
Run;
```

For the impact of circadian rhythm, the syntax with SAS using the MIXED procedure will be:

```
Proc mixed data= ... covtest method=REML;
  Class patient treatment time visit country;
  Model changeIOP = treatment time visit country washoutdur treatment*time
    treatment*visit / solution;
  Repeated visit / subject= patient(time) type=unstructured;

  Estimate 'Week 12 8am - Diff T4032 - Lumigan' treatment 1 -1
    treatment*time 0 0 1 0 0 -1 treatment*visit 0 1 0 -1 / cl;
  Estimate 'Week 12 10am - Diff T4032 - Lumigan' treatment 1 -1
    treatment*time 1 0 0 -1 0 0 treatment*visit 0 1 0 -1 / cl;
  Estimate 'Week 12 4pm - Diff T4032 - Lumigan' treatment 1 -1
    treatment*time 0 1 0 0 -1 0 treatment*visit 0 1 0 -1 / cl;
  Estimate 'Week 6 8am - Diff T4032 - Lumigan' treatment 1 -1
    treatment*time 0 0 1 0 0 -1 treatment*visit 1 0 -1 0 / cl;
  Estimate 'Week 6 10am - Diff T4032 - Lumigan' treatment 1 -1
    treatment*time 1 0 0 -1 0 0 treatment*visit 1 0 -1 0 / cl;
  Estimate 'Week 6 4pm - Diff T4032 - Lumigan' treatment 1 -1
    treatment*time 0 1 0 0 -1 0 treatment*visit 1 0 -1 0 / cl;

  Estimate 'Week 12 8am - T4032' intercept 1 treatment 1 0
    time 0 0 1 visit 0 1 treatment*time 0 0 1 0 0 0
    treatment*visit 0 1 0 0 washoutdur xxx*/ cl;
  Estimate 'Week 12 10am - T4032' intercept 1 treatment 1 0
    time 1 0 0 visit 0 1 treatment*time 1 0 0 0 0 0
    treatment*visit 0 1 0 0 washoutdur xxx*/ cl;
  Estimate 'Week 12 4pm - T4032' intercept 1 treatment 1 0
    time 0 1 0 visit 0 1 treatment*time 0 1 0 0 0 0
    treatment*visit 0 1 0 0 washoutdur xxx*/ cl;
  Estimate 'Week 12 8am - Lumigan' intercept 1 treatment 0 1
    time 0 0 1 visit 0 1 treatment*time 0 0 0 0 0 1
    treatment*visit 0 0 0 1 washoutdur xxx*/ cl;
  Estimate 'Week 12 10am - Lumigan' intercept 1 treatment 0 1
    time 1 0 0 visit 0 1 treatment*time 0 0 0 1 0 0
    treatment*visit 0 0 0 1 washoutdur xxx*/ cl;
  Estimate 'Week 12 4pm - Lumigan' intercept 1 treatment 0 1
    time 0 1 0 visit 0 1 treatment*time 0 0 0 0 1 0
    treatment*visit 0 0 0 1 washoutdur xxx*/ cl;
```

```
Estimate 'Week 6 8am - T4032' intercept 1 treatment 1 0
time 0 0 1 visit 1 0 treatment*time 0 0 1 0 0 0
treatment*visit 1 0 0 0 washoutdur xxx*/ cl;
Estimate 'Week 6 10am - T4032' intercept 1 treatment 1 0
time 1 0 0 visit 1 0 treatment*time 1 0 0 0 0 0
treatment*visit 1 0 0 0 washoutdur xxx*/ cl;
Estimate 'Week 6 4pm - T4032' intercept 1 treatment 1 0
time 0 1 0 visit 1 0 treatment*time 0 1 0 0 0 0
treatment*visit 1 0 0 0 washoutdur xxx*/ cl;
Estimate 'Week 6 8am - Lumigan' intercept 1 treatment 0 1
time 0 0 1 visit 1 0 treatment*time 0 0 0 0 0 1
treatment*visit 0 0 1 0 washoutdur xxx*/ cl;
Estimate 'Week 6 10am - Lumigan' intercept 1 treatment 0 1
time 1 0 0 visit 1 0 treatment*time 0 0 0 1 0 0
treatment*visit 0 0 1 0 washoutdur xxx*/ cl;
Estimate 'Week 6 4pm - Lumigan' intercept 1 treatment 0 1
time 0 1 0 visit 1 0 treatment*time 0 0 0 0 1 0
treatment*visit 0 0 1 0 washoutdur xxx*/ cl;
```

run;

* xxx= *Mean of washout duration values in the population*

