1.5 Sample size considerations

The sample size determination was based on the primary efficacy endpoint, *i.e.*, the change in IOP at the three time points (08:00, 10:00, 16:00) after 12 weeks of treatment, in the worse eye.

Non-inferiority of T4032 *versus* Lumigan® 0.01% will be tested with a non-inferiority margin of 1.5 mmHg. Non-inferiority will be concluded if it is achieved for each of the three time points 08:00, 10:00 and 16:00.

The evaluation will be based upon a two-sided 95% confidence interval (CI) on the difference in mean change in IOP after 12 weeks of treatment.

With data available for 180 patients in each arm, there is more than 90% power to show that the T4032 unpreserved eye drops is non-inferior to Lumigan® 0.01% preserved eye drops. The hypothesis was based on the 1.5 mmHg margin, assuming no difference between the two groups (average difference of 0 mmHg), and a standard deviation of 3 mmHg and correlation between time-points of 0.7 on the primary efficacy variable.

Evaluable patients are defined as randomised patients having received at least one dose of IMP (T4032 or Lumigan®) and with at least one post-randomisation efficacy assessment.

Accounting for a 10% dropout/non-evaluable rate, 400 initially treated patients were expected to be randomised.

The sample size of 400 randomised patients is also justified to collect enough safety data. Number of screened patients depends on the screen failure rate and was estimated at 668 patients.

At the end of the recruitment period, 723 patients were screened and 485 patients were randomised.

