6.1.4 Exploratory analysis of the primary efficacy endpoint

Possible covariate effect (Possible impact of COVID-19 pandemic) will be investigated in the MMRM model (resp. in the ANCOVA model for the sensitivity analysis). Covariate of interest and covariate by treatment interaction will be added to the main model on the m-ITT set.

The tests for interactions will be interpreted at the 7% level of significance.

The adjusted mean difference between treatment groups will be computed. If the p-value is lower than 7% and the interaction is qualitative, then the main model will be performed by inclusion period.

The impact of circadian rhythm will also be assessed by using time factor within the model, as patient nested in time, i.e. the model will include as fixed factors, treatment, scheduled visit time point (Week 6 and Week 12), time (8:00, 10:00 and 16:00), wash-out duration, country as covariates, treatment by visit interaction, treatment by time interaction, and patient nested in time. The adjusted mean treatment differences (T4032 - Lumigan® 0.01%) and their corresponding 95% CI will be estimated at each time at Week 12.

The syntax with SAS using the MIXED procedure is detailed in [Appendix 1](#).

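### The exploratory circadian model treats the 08:00, 10:00 and 16:00 readings of one eye as independent, so its Type III p-values for treatment and treatment-by-time are invalid

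*SAP*

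**What the plan says.** SAP 6.1.4 adds an exploratory model for circadian rhythm. Its fixed effects are treatment, visit, clock time, wash-out duration and country, and the text closes the list with "treatment by visit interaction, treatment by time interaction, and patient nested in time". The output it names is the adjusted treatment difference, whose "95% CI will be estimated at each time at Week 12". Section 6.2.1 uses the same model at Week 6.

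The code in Appendix 1, item 4 has "Model changeIOP = treatment time visit country washoutdur treatment*time" plus treatment-by-visit, and one covariance line, "Repeated visit / subject= patient(time) type=unstructured". There is no RANDOM statement. The shells of Tables 4.70 and 4.117 print a p-value at each clock time and Type III p-values that include treatment, treatment-by-visit and treatment-by-time.

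SAP 1.5 assumes an SD of 3 mmHg and a "correlation between time-points of 0.7 on the primary efficacy variable". The primary MMRM (SAP 6.1.1; Appendix 1, item 1) is fitted separately for each clock time with "Repeated visit / type = UN subject = patient".

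**The concern.** In PROC MIXED, observations from different subjects are independent unless a RANDOM statement links them. With patient-within-time as the subject, Week 6 and Week 12 at the same clock time share a 2x2 unstructured block, but the covariance between clock times in the same eye is fixed at zero. The prose in 6.1.4 describes the same nesting, so this is not a coding slip that the text overrides.

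Ignoring a positive correlation has opposite effects on two kinds of contrast. An average over clock times (treatment) gets a standard error that is too small. A difference between clock times (treatment-by-time) gets one that is too large. Treatment-by-time is the term that tests whether the treatment difference changes through the day. A reader of Table 4.70 would take a non-significant result as reassurance of a uniform effect, when the test as coded can hardly reject.

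**Working it through.** **Inputs from the SAP.** SD 3 mmHg, correlation r = 0.7 between clock times, 180 evaluable per arm, margin 1.5 mmHg (all 1.5); three clock times and two post-baseline visits; 1:1 allocation (1.4.2.1).

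**Assumed, not in the documents.** Equal variances, complete data and no covariate effects. The correlation between visits at the same clock time, rv, runs from 0.3 to 0.7. The correlation between different clock times at different visits, rc, is either separable (rc = 0.7 × rv) or one of several non-separable values.

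**The plan's own figure.** The standard error of a difference is 3 × √(2/180) = 0.316. Power is 99.7% at one clock time and 99.3% for all three at correlation 0.7, so the stated power above 90% is met.

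**Standard errors.** Let k = 9 × 2/180 = 0.1. The table takes rv = 0.6 and rc = 0.42.

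| Contrast | Variance the model assumes | True variance | SE, model / true |
|---|---|---|---|
| Treatment (mean of six cells) | k(1+rv)/6 = 0.0267 | k(1+2r+rv+2rc)/6 = 0.064 | 0.163 / 0.253 |
| Treatment-by-time (two clock times) | k(1+rv) = 0.160 | k(1−r+rv−rc) = 0.048 | 0.400 / 0.219 |
| Treatment-by-visit | 2k(1−rv)/3 = 0.0267 | 2k(1+2r−rv−2rc)/3 = 0.064 | 0.163 / 0.253 |
| Week 12, one clock time | 0.080 + 0.0267/4 = 0.0867 | 0.080 + 0.064/4 = 0.096 | 0.294 / 0.310 |

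In the last row, 0.080 is k(1+rv)/2. It is the variance of the mean over visits at one clock time and is the same in both columns.

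**True size of a nominal 5% test.**
- Treatment: variance ratio 0.064/0.0267 = 2.4, so the size is 2 × (1 − Φ(1.96/√2.4)) = 20.6%.
- Treatment-by-time (2 df): ratio 0.048/0.160 = 0.30, so the size is P(χ²₂ > 5.99/0.30) = 0.0046%.
- Treatment-by-visit: 20.6%.
- Week 12, one clock time: 2 × (1 − Φ(1.96 × 0.294/0.310)) = 6.3%.

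**Dependence on the assumptions.**
- In any separable case with r = 0.7, the first three sizes do not depend on rv.
- Non-separable cases:

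| rv | rc | Treatment | Treatment-by-time |
|---|---|---|---|
| 0.7 | 0.40 | 19.6% | 0.02% |
| 0.6 | 0.60 | 22.6% | below 0.0001% |
| 0.7 | 0.65 | 22.3% | below 0.0001% |

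- Treatment-by-visit is sensitive to rc. It is 25.8%, 11.0% and 9.0% in those three cases, becomes exact at rc = 0.7 and turns conservative above that.
- With rv from 0.3 to 0.7 and rc at or above the separable value, up to the smaller of rv and 0.65, the Week 12 size is 5.2 to 7.5%, with intervals 1 to 9% too narrow.
- If the clock-time correlation were only 0.3 (separable), treatment would still be at 12.1% and treatment-by-time at 1.4%.

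**Power of treatment-by-time.** For a departure δ at one clock time at both visits, the noncentrality is λ = (2/3)δ² ÷ (true contrast variance/2). At δ = 0.75 and rv = 0.6, λ = 0.375/0.024 = 15.6. Power is P(χ²₂(λ) > 5.99/0.30) = 35% as coded and P(χ²₂(λ) > 5.99) = 95% with the correct covariance. The ranges below are for rv = 0.6 down to 0.3, separable. SAP 1.5 reports that "723 patients were screened and 485 patients were randomised", which is about 242 per arm; the evaluable number is not given.

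| Per arm | δ (mmHg) | As coded | Correct covariance |
|---|---|---|---|
| 180 | 0.50 | 5–8% | 65–75% |
| 180 | 0.75 | 35–51% | 95–98% |
| 242 | 0.50 | 10–17% | 79–87% |
| 242 | 0.75 | 59–77% | about 99% |

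**Simulation check** (4,000 null trials, 180 per arm, rv 0.5, rc 0.35, covariance estimated). As coded, the rejection rates were treatment 20.5%, treatment-by-time 0 of 4,000, treatment-by-visit 21.7% and Week 12 at 08:00 6.5%. With a 6x6 unstructured matrix per patient they were 4.8%, 5.1%, 5.4% and 4.8%.

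**The case against.** The strongest reply concerns weight. Section 6.1.4 promises only the treatment differences and intervals at each clock time, and those are nearly right. The badly wrong p-values are rows in table shells with no interpretation rule attached. The 7% interaction rule in that section follows the COVID-19 covariate text. The analysis is exploratory and was added in the SAP (Section 8). All of this stands and sets the priority, but it does not make the printed p-values valid.

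The contrast with the primary model is also weaker evidence than it looks. That model sees one clock time per run, so its subject definition says nothing about correlation across clock times. The real evidence is the 0.7 in Section 1.5.

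Two neighbouring points should be kept apart from this error. Section 3.5 asks for baseline IOP and the COVID-19 class in the models, and the circadian model has neither. The COVID-19 class is missing from the main MMRM as well, so that conflict runs through the whole SAP. The twelve per-arm statements, such as "Estimate 'Week 12 8am - T4032' intercept 1 treatment 1 0", list no country coefficients although country is a CLASS effect. Whether they are estimable depends on how the software fills unlisted coefficients, which the documents do not state.

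**Conclusion.** The concern holds. As written, the model fixes at zero a correlation that the SAP itself puts at 0.7. The treatment p-value is much too liberal (about 20 to 23% at nominal 5%) and the treatment-by-time p-value is far too conservative (about 0.02% or less). These sizes assume equal variances, complete data and the between-visit correlations shown. The direction of both errors follows from any appreciable positive correlation between clock times. Treatment-by-visit is usually too liberal, but that depends on a correlation the documents do not give. The Week 12 intervals by clock time are mildly too narrow at most of the values considered.

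No decision depends on this output, and the non-inferiority conclusion comes from three separate models that are unaffected. It is a low-priority correction.

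**What to change.** Make the patient the subject. Use REPEATED time*visit with SUBJECT=patient and TYPE=UN over the six cells (21 parameters), or REPEATED time visit with TYPE=UN@UN if a separable form is acceptable. In 6.1.4, replace the nesting phrase with wording that says clock time and visit are both repeated within patient. Adding ddfm=satterth would match the main model, but it is a matter of consistency and not part of the error.

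The cost is one line of code and one phrase, with data already collected. The six treatment-difference ESTIMATE statements stay as they are.

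Separately, reconcile the covariates with Section 3.5 (the COVID-19 class across the SAP, baseline IOP in this model). Also check that the twelve per-arm ESTIMATE statements are estimable, or write the country weights out. If baseline IOP or the COVID-19 class is added, those statements will need coefficients for them.
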